## 4.2 PRIMARY ESTIMAND ANALYSIS

Hypothesis test for the primary estimand is described in Section 2.1.

Five attributes of the primary estimand are provided in Table 1. Further details on the definition of the Endpoint attribute are provided in Section 4.2.1. Information on primary estimator, intercurrent events and their handling as well as the handling of missing data is described in Section 4.2.2, Section 4.2.3 and Section 4.2.4 describe sensitivity and supplementary analysis for the primary estimand.

### 4.2.1 Definition of Primary Endpoint

The primary efficacy endpoint is time to onset of cCDP12, defined as the first occurrence of a CDP event according to at least one of the following three criteria:

- **C1:** CDP12, defined as a 12-week confirmed increase from baseline in EDSS score of  $\geq 1.0$  point in patients with a baseline EDSS score of  $\leq 5.5$  or a 12-week confirmed increase  $\geq 0.5$  points in patients with a baseline EDSS score of  $> 5.5$ , or
- **C2:** CIT25FWT12, defined as a 12-week confirmed increase of  $\geq 20\%$  from baseline in T25FWT score, or
- **C3:** CI9-HPT12, defined as a 12-week confirmed increase of  $\geq 20\%$  from baseline in time to complete the 9-HPT score.

Four conditions must be fulfilled to satisfy the 12-weeks confirmation criteria for disability progression based on C1, C2 and C3:

1. The confirmation (of disability progression) visit must be at least 12 weeks (84 days) after the initial disability progression.
2. The confirmation visit must be either a scheduled or treatment discontinuation visit.
3. Assessments within 30 days after the onset of a protocol-defined relapse cannot be used for confirmation of the progression.
4. All EDSS, T25FWT or 9-HPT assessments between the initial disability progression and the confirmation visit should also fulfill the requirements of disability progression, i.e.,  $\geq 1.0$  point increase in baseline EDSS if baseline EDSS  $\leq 5.5$  or  $\geq 0.5$  increase if baseline EDSS  $> 5.5$ , or  $\geq 20\%$  increase in T25FWT or 9-HPT from baseline.

If any of the four criteria listed above are not satisfied, then the initial disability progression is not a CDP. In criteria 3, a **protocol-defined relapse** is defined as the occurrence of new or worsening neurological symptoms attributable to MS and immediately preceded by a relatively stable or improving neurological state of at least 30 days. Symptoms must persist for at least 24 hours and should not be attributable to confounding clinical factors (e.g., fever, infection, injury, adverse reactions to concomitant medications). The new or worsening neurological symptoms must be

accompanied by objective neurological worsening consistent with an increase of at least one of the following:

- Half a step (0.5 point) on the EDSS
- Two points on one of the selected FSS as listed below
- One point on two or more of the selected FSS as listed below

The change must affect the following selected FSS: pyramidal, ambulation, cerebellar, brainstem, sensory, or visual. Episodic spasms, sexual dysfunction, fatigue, mood change, or bladder or bowel urgency or incontinence will not suffice to establish a relapse.

An independent Examining Investigator at each study site will assess EDSS, T25FWT and 9-HPT for all patients at the site at screening, baseline, every 12 weeks (regularly scheduled visit) during the blinded treatment period of the study, during the SFU period, and at withdrawal-from-treatment and end-of-study visits. Additional assessments for individual patients may be requested between visits (i.e., during an MS relapse). Initial disability progression can occur at any visit, including unscheduled visits.

The Examining Investigator is not the physician responsible for the patient care (the Treating Investigator).

The EDSS (2011 Version 04/10.2) is based on a standard neurological examination, incorporating functional systems (visual, brainstem, pyramidal, cerebellar, sensory, bowel and bladder, and cerebral [or mental]) that are rated and then scored as a FSS, and ambulation, which is scored as ambulation score. Each FSS is an ordinal clinical rating scale ranging from 0 to 5 or 6 and an ambulation score that is rated from 0 to 16. These ratings are then used in conjunction with observations, as well as information, concerning ambulation and use of assistive devices to determine the total EDSS score. The total EDSS score ranges from 0 (normal) to 10.0 (death) in 0.5-point steps. All FSS, ambulation score, and total EDSS scores will be captured electronically and the Neurostatus-eEDSS definitions and calculating algorithms will be used ([D'Souza et al. 2017](#)). Under this approach, all subscores are required (meaning they are compulsory and data entry is required) and all subscores always contribute to the scoring algorithm with the following exceptions:

- Cerebral FS
  - Fatigue

The following subscores are always optional (meaning data entry is not required), but if a value for one side (right or left) is entered, the other is also required. In other words, the user must either enter both right and left values, or neither. When both right and left values are entered, they always contribute to the scoring algorithm:

- Visual FS
  - Disc Pallor
- Pyramidal FS
  - Palmomental Reflex

The following subscores are always optional, and they never contribute to the scoring algorithm:

- Pyramidal FS
  - Pronator Drift – pronation
  - Pronator Drift - downward drift
  - Position Test – sinking
  - Walking on Heels
  - Walking on Toes
  - Hopping on One Foot
  - If able to lift only one leg at a time: (grade in degrees)
- Sensory FS
  - Lhermitte's Sign
  - Paraesthesiae UE
  - Paraesthesiae trunk
  - Paraesthesiae LE
- Bowel & Bladder FS
  - Sexual Dysfunction
- Ambulation
  - Distance reported by the patient
  - Time reported by the patient

The T25FWT test is a performance measure used to assess walking speed based on a timed 25-foot walk. The patient is directed to start at one end of a clearly marked 25-foot course and is instructed to walk 25 feet as quickly and safely as possible. The Examining Investigator will time the patient from the start of the walk to the end of the 25 feet. The task is immediately administered again by having the patient walk back the same distance. The score for the T25FWT is the average of the two completed trials.

Patients may use assistive devices (e.g., cane, crutch, or rollator) when performing the task. The Examining Investigator should assess which assistive device is necessary and try to use the same assistive device at each study visit, whenever possible. Non-wheeled walkers should not be used. Circumstances that may affect the patient's performance, or if the patient cannot complete the T25FWT twice, should be reported.

If the test results for T25FWT are not available due to a "physical limitation," the maximum possible value for the scale (180 seconds) will be imputed. If one of the two trials is not available and not missing due to a "physical limitation," the result from the other trial will be used to impute the missing value. Very low values will be considered to be outliers. For outliers, the following rules will be applied. Values below the lower bound will be treated as missing, and the imputation rule will be applied as defined above. The lower bound is 2.2 seconds ([Bohannon 1997](#)).

The 9-HPT is a performance measure to assess upper limb function. It consists of a container containing nine pegs and a wood or plastic block containing nine empty holes. The patient is to pick up each of the nine pegs one at a time and as quickly as possible place them in the nine holes. Once all the pegs are in the holes, the patient is to remove them again one at a time as quickly as possible and replace them into the container. The total time to complete the task is recorded. Both the dominant and non-dominant hands are tested twice (two consecutive trials of the dominant hand, followed immediately by two consecutive trials of the non-dominant hand). The score for the 9-HPT is an average of the four trials. The two trials for each hand are averaged, converted to the reciprocal of the mean time for each hand, and then the two reciprocals are averaged and back-transformed to the original scale (i.e., by taking another reciprocal).

If the test results for 9-HPT are not available due to a "physical limitation," the maximum possible value for the scale (300 seconds) will be imputed. If one of the two trials for the dominant and non-dominant hand is not available and not missing due to a "physical limitation," the result from the other trial will be used to impute the missing value. Very low values will be considered to be outliers. For outliers, the following rules will be applied. Values below the lower bound will be treated as missing, and the imputation rule will be applied as defined above. For 9-HPT, the lower bound is 10 seconds ([Oxford Grice et al. 2003](#)).

#### **4.2.1.1 cCDP in the Presence of Differential Right Censoring**

A complicating factor for defining cCDP is the presence of differential right censoring in the individual components, i.e., time to onset of CDP, CIT25FWT and CI9-HPT. In such circumstances, the following algorithm will be used to define cCDP:

1. If the onset times of the individual components are all observed, then the onset time of cCDP is the earliest of the observed onset times of the individual components,

2. Otherwise if all onset times of the individual components are right censored, then the onset time of cCDP12 is right censored at the earliest of the right censored onset times of the individual components,
3. Otherwise if the earliest of the observed onset times occurs prior *or equal* to the earliest of the right censored onset times of the individual components, then the onset time of cCDP is the earliest of the observed onset times of the individual components,
4. Otherwise if the earliest of the observed onset times occurs after the earliest of the right censored onset times of the individual components, then the onset time of cCDP is set to the earliest of the observed onset times of the individual components.

In scenario 4, the approach to specify the onset time of cCDP as the earliest of the observed onset times of the individual components can in some cases overestimate the true onset time. Nonetheless, the proposed approach is pragmatic and reasonable because it leads to an estimate of the proportion of cCDP events by the end of the study that is at least as large as the observed proportion, and it has a negligible impact on treatment effect estimation if the independent censoring assumption is plausible for the individual components.

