Patients without any prior progression events during the DBT phase will be censored at their last EDSS, 9-HPT, or T25FWT assessments (administrative censoring).

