In the absence of sufficient data to perform the multiple imputation described above (i.e., at least 5% of patients should have at least one EDSS/T25FWT/9HPT assessment after treatment discontinuation), the robustness of the independent censoring assumption will be evaluated using a tipping point analysis.

Multiple imputation will be used to either impute a progression event or to censor the time to onset of confirmed progression at their last EDSS, T25FWT or 9 - HPT assessment prior to withdrawal from the study. The presence or absence of a progression event at the last EDSS, 9-HPT, or T25FWT assessment prior to withdrawal from the study will be imputed from a Bernoulli distribution with success probability ranging from 0-1 in increments of 0.33. This procedure will be applied within arms followed by treatment effect estimation in 100 imputed data sets. An overall estimate of the treatment effect and associated standard error will be estimated as described in sensitivity analysis 1. The scenarios that result in non-significant treatment effect estimates will be identified for a tipping point analysis.

3. The primary analysis will be conducted using actual study days to estimate cCDP12 event times and treatment effects. Due to the periodic nature of assessments, the exact timing of cCDP12 events is unknown, as events are recorded at the next scheduled assessment after the event, resulting in interval-censored data. To assess the potential impact of using actual event days on estimation and hypothesis testing, a sensitivity analysis using interval censoring methods will be performed.

For each patient, the left and the right boundaries of the interval will be derived based on the following rules:

Situations	Left Boundary	Right Boundary
Patients who had cCDP12	The date of the last assessment that showed a disease progression-free* status	The date of the first assessment that showed cCDP12
Patients who did not have cCDP12	The date of the last assessment that showed a disease progression-free* status	Not applicable (Missing)
Patients who died and did not have cCDP12 prior to death	The date of the last assessment that showed a disease progression-free* status	Death date

cCDP12= 12-week composite confirmed disability progression

\* For patients who did not have any post-baseline assessment with disease progression-free status, the left boundary is the date of randomization.

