- No Diagnosis of RMS (i.e., relapsing-remitting multiple sclerosis or active secondary progressive multiple sclerosis where patients still experience relapses) in accordance with the revised McDonald Criteria 2017
- Less than two documented clinical relapses within the last 2 years prior to screening, or no clinical relapse in the year prior to screening (with no relapse 30 days prior to screening and at baseline)
- Not neurologically stable within 30 days prior to randomization and baseline assessments
- EDSS scores at screening and baseline greater than 5.5
- Average T25FWT score over two trials at screening and over two trials at baseline respectively, above 150 seconds
- Average 9-HPT score over four trials at screening and over four trials at baseline respectively, above 250 seconds

- No documented MRI of brain with abnormalities consistent with MS at screening
- Randomized to the higher dose arm and with an incorrect classification of body weight into the strata  $<75$  kg or  $\geq 75$  kg

In addition, the hypothetical strategy will be used to handle the following intercurrent events:

- Early discontinuation from study treatment
- Initiation of approved MS DMT medication
- Two consecutive missed assessments of EDSS, T25FWT and 9-HPT
- Erroneously received a quantity of ocrelizumab (including no ocrelizumab) other than the group to which the patient was randomized
- Received study drug that had been mishandled (e.g., incorrect storage temperature) and was not approved for subsequent use
- Received ocrelizumab / ocrelizumab placebo but was not randomized

Under this strategy, the data after these intercurrent events will be treated as missing and the time to onset of cCDP12 will be censored at the last assessments prior to the intercurrent event times. However, the observed data after the intercurrent events will still contribute to the confirmation period for determining if an initial progression can be confirmed. This analysis estimates the treatment effect of the higher dose of ocrelizumab in a population who always receives the study treatment as planned and without consecutive missing assessments of the primary endpoint.

2. The primary analysis will be repeated after removing the individual components from cCDP12 one at a time. This analysis will determine the extent to which the treatment effect is driven solely by each of the individual components.

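### cCDP12 censoring rules 2 and 4 keep follow-up after the first lost test only when an event follows, so the hazard ratio can shift if test loss differs between arms

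*SAP*

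**What the plan says.** SAP Section 4.2.1.1 gives four rules for building the composite when its three components are censored at different times.

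- Rule 2, no component event: "then the onset time of cCDP12 is right censored at the earliest of the right censored onset times of the individual components".
- Rule 4, first observed onset later than the first component censoring time: "then the onset time of cCDP is set to the earliest of the observed onset times of the individual components".

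The section accepts that rule 4 can place the onset too late, and defends it on the ground that "it has a negligible impact on treatment effect estimation if the independent censoring assumption is plausible for the individual components".

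Section 4.2.2 has a general censoring sentence: "Patients without any prior progression events during the DBT phase will be censored at their last EDSS, 9-HPT, or T25FWT assessments". It does not say whether the earliest or the latest of the three dates is meant.

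**The concern.** Take a hypothetical patient whose T25FWT stops at Week 48 while EDSS and 9-HPT continue to Week 168. With no progression, rule 2 ends follow-up at Week 48. With a confirmed EDSS progression at Week 120, rule 4 keeps the patient at risk to Week 120 and counts the event. Whether Weeks 48 to 120 are counted depends on the outcome.

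Dropping event-free time while keeping the events inflates the apparent hazard in any arm where a test is lost. If both arms are inflated equally, the HR is nearly unchanged. If not, the arm with more loss looks worse. The SAP's stated condition, independent censoring of each component, does not exclude this.

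The primary HR is at stake, in either direction. cCDP24 and cCDP48 in the confirmatory hierarchy are built the same way. A Kaplan-Meier incidence of cCDP12 would be biased upward even with balanced loss, although Section 4.2.2 specifies only the HR and the log-rank test.

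**Working it through.** **The plan's own figure.** Events for HR 0.66, 80% power, two-sided 5% and 2:1 allocation (SAP 2.2): (1.960 + 0.842)² / [(1/3)(2/3)(ln 0.66)²] = 7.849 / 0.03837 = 204.6, so 205 is reproduced. The standard error (SE) of log HR at 205 events is √(9 / (2 × 205)) = 0.148.

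**Control hazard.** SAP 2.2 gives 21.5% control progression without a period. Read as 96 weeks (1.840 years), the hazard is −ln(0.785) / 1.840 = 0.132 per year. With 786 patients, 390 recruited per year, 5% annual dropout and the 226-week blinded phase (protocol 3.2), this gives 205.9 expected events. Read as two years, it gives 191.9.

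**Model A: constant annual loss of one test.** Assumptions: the design above; three equal, independent exponential components; one randomly chosen component lost at a constant rate, independently of outcome; 6 million patients per scenario. The SAP's independence condition holds by construction. Consistent censoring means that every patient is censored at the first component loss.

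| Annual loss, control / higher dose | SAP rules, true HR 1.00 | SAP rules, true HR 0.66 | Consistent censoring, true HR 0.66 |
|---|---|---|---|
| none | 1.001 | 0.658 | 0.658 |
| 5% / 5% | 1.000 | 0.661 | 0.659 |
| 10% / 10% | 0.999 | 0.662 | 0.659 |
| 5% / 2% | 0.972 | 0.643 | 0.661 |
| 2% / 5% | 1.029 | 0.680 | 0.659 |
| 10% / 5% | 0.951 | 0.630 | 0.662 |
| 10% / 2% | 0.925 | 0.611 | 0.661 |
| 2% / 10% | 1.085 | 0.716 | 0.658 |

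The crude control hazard shows why. Under SAP rules it rises from 0.1315 with no loss to 0.1378 at 5% and 0.1444 at 10% annual loss; under consistent censoring it stays at about 0.132. With no true effect, 10% loss in control and 5% in the higher-dose arm should give about 0.1378 / 0.1444 = 0.954; the simulated HR is 0.951.

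In SE units at true HR 0.66, 2% / 5% gives ln(0.680 / 0.658) / 0.148 = 0.22, and 2% / 10% gives ln(0.716 / 0.658) / 0.148 = 0.57. Under the null, rejection in favour of the higher dose is 3.0% with no loss (simulated) and 4.5% at 5% / 2%.

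**Model B: a fixed share of patients loses one test.** Assumptions: follow-up pattern from SAP 2.2 and 2.3; 12-week visits; confirmation on the same test; component shares 0.40 / 0.35 / 0.25; 1,000,000 control and 2,000,000 higher-dose patients. The gap is the time by which the lost test ends early. The complete-data HR is 0.659.

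| Share affected, control / higher dose | Rule | 24-week gap | 48-week gap | 48–120-week gap |
|---|---|---|---|---|
| 15% / 5% | SAP | 0.655 | 0.649 | 0.641 |
| 15% / 5% | consistent | 0.658 | 0.659 | 0.660 |
| 5% / 15% | SAP | 0.662 | 0.668 | 0.678 |
| 5% / 15% | consistent | 0.659 | 0.658 | 0.658 |
| 6% / 2% | SAP | 0.657 | 0.655 | 0.652 |

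The largest shift in this table is about 0.19 SE: ln(0.641 / 0.659) / 0.148 = −0.19. Other component shares, or reaching 21.5% at 48 or 144 weeks, give at most 0.21 SE. Balanced loss gives 0.658 to 0.660 throughout. With balanced loss, control incidence at Week 168 is 33.2% against 33.0% under consistent censoring (10% affected, 24-week gap), and 34.8% against 32.9% (20% affected, 48–120 weeks).

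At 15% / 5% with 48–120-week gaps, cCDP24 gives 0.643 (complete data 0.658) and cCDP48 gives 0.651 (complete data 0.660).

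**How long a gap is needed.** On scheduled visits, rule 4 needs onset 12 weeks after the lost test's last date and confirmation 12 weeks after that, so about 24 weeks. Because "Initial disability progression can occur at any visit, including unscheduled visits", a gap just over 12 weeks can suffice; the smallest simulated was 85 days. With one missed visit and 10% of patients affected, rule 4 events are at most 0.011% of all events and the HR does not change. A test missed and later resumed has no effect.

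**Do the planned analyses isolate the rule?**

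- Supplementary analysis 1 censors at "Two consecutive missed assessments of EDSS, T25FWT and 9-HPT". If this means all three tests, losing one never triggers it and the HR stays at 0.641 (15% / 5%, long gaps). If it means any one test, the HR is 0.660, but the analysis also changes the population and other intercurrent events.
- Supplementary analysis 2: "The primary analysis will be repeated after removing the individual components from cCDP12 one at a time". In the same scenario it removes about half the shift (0.649 to 0.650 against 0.658 to 0.659), while changing the endpoint.
- Sensitivity analysis 3 changes the estimator. Its left boundary, "The date of the last assessment that showed a disease progression-free* status", does not say which component's assessment counts.
- Sensitivity analyses 1 and 2 concern study withdrawal.
- The planned table of missed assessments (SAP 4.6.3, Appendix 1) is by country, not arm.

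**The case against.** The strongest reply is that the damaging input is implausible here. Both arms receive blinded ocrelizumab on one schedule, and the assessor is blinded and kept away from safety data. All three tests fall at the same 12-weekly visits, on a device that presents them in a set order. Inability to perform a timed test is scored at 180 or 300 seconds, so the likeliest reason for losing one test is already handled. Study withdrawal and data cutoff normally end all three together. At 6% loss in control and 5% in the higher-dose arm with 48–120-week gaps, the HR is 0.6605 against 0.6619, about 0.01 SE. The 10% against 2% annual scenario implies losing one test in 1 − 0.9⁴ = 34% of one arm over four years, which is extreme. The SAP also discloses rule 4, and the single-test endpoints CDP12, CIT25FWT12 and CI9-HPT12 do not depend on these rules.

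All of this stands as an argument about size, and it is why the point is minor. It does not make the SAP's condition sufficient. The planned outputs would not show whether loss was balanced, and no planned analysis changes only this rule.

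**Conclusion.** The point holds and is minor. Rules 2 and 4 make follow-up after the first lost test depend on outcome. The negligible-impact statement is right for the HR only if component loss is also balanced between arms; the balanced scenarios then moved the HR by about 0.003 at most.

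Under unequal loss the arm with more loss looks worse. The shift is about 0.2 SE of log HR at 15% against 5% of patients with long gaps, or at 5% against 2% per year. It reaches about 0.6 SE only under the extreme annual rates. All loss rates and gaps are assumptions, as are independent component event times and the 96-week reading of 21.5%. Positively correlated components gave the same pattern: with no true effect, HR 0.925 at 10% control / 2% higher-dose annual loss, and 1.080 reversed. The 205-event target is unaffected.

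**What to change.** Keep rules 1 to 4 as the primary derivation, and:

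1. Add a sensitivity analysis for cCDP12, cCDP24 and cCDP48: censor each patient at the earliest component censoring time unless a confirmed event has its onset at or before that time.
2. Tabulate by arm the patients with differing component end dates, the gap lengths and the number of rule 4 events.
3. Add to the negligible-impact sentence that component loss must be balanced between arms.
4. As editorial points, cross-refer the Section 4.2.2 censoring sentence to rule 2, and state whether the missed-assessment criterion in supplementary analysis 1 means all three tests or any one.

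The cost is one extra run per endpoint, one table and short wording changes, with no new data. The sensitivity run should not replace the primary rule, because it leaves out confirmed events: 0.5% to 6.2% of them in the balanced scenarios, about 1 to 13 of 205 to 210. It also loses power (0.768 against 0.810 at 10% annual loss in both arms). It is not exact for cCDP48 under unequal loss (0.665 against 0.660 with complete data).

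The cutoff was scheduled for December 2024 (SAP 2.3) and SAP version 4 was signed on 18 February 2025. If treatment codes are already open, the run must be labelled post hoc. Aligning rule 4 with rule 2 in the primary analysis is an option only if they are still closed.
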